5.3. Data sources that will be used to collect data about subjects:10

Instruments. The objective of this proposal is to determine the clinical value of the PRISM intervention among adolescents with T1D and their families. Specifics for the proposed measures, by Aim, are below and in **Table 2a and 2b**.

Aim 1 Measures. HbA1C is collected at every in-person clinic visit as standard of care across both sites from trained medical staff drawing blood samples using the fingerstick method. Blood assays are analyzed immediately using the DCA 2000 Hemoglobin HbA1C system (Siemens-Bayer). Patients with virtual clinic visits and/or no Hba1c recorded within the prior 4 weeks will collect a dried blood spot sample and mail to the central in advance of their appointment. The HbA1c on filter paper is extracted and measured on the Vitros 4600 HbA1c assay. This assay is correlated with the DCA 2000. Although we will not have a central lab, both sites are using the same point-of-care machines and lab tests which alleviates the cost-burden of a central lab and also mimics other large, multisite studies (e.g., T1D Exchange and SEARCH for Diabetes in Youth). HbA1C will be tracked at each visit after enrollment from their medical record or an athome A1c blood spot test kit will be provided for the patient, which has been routinely incorporated into care at Seattle Children's since May of 2020. Given recent consensus reports recommending attention to additional glycemic metrics beyond HbA1c, for those patients using CGMs, we will also collect time in range (percentage of readings in the range of 70-180 mg/dL).⁵¹ All CGM data will be downloaded using standard CGM device-reading software available. Patients will be asked to share their CGM code with us the same way they do with their providers, which is part of usual clinical care.

Protocol Version Number: 10 Protocol Version Date: 7/28/2021

Table	Table 2a. Data collection instruments (Adolescent)								
Aim	Construct	Measure	Source (and Time in months)						
1	Glycemic control	HbA1C	Chart review or At-Home A1c Kit						
	Time in Range	CGM download	Device download						
	Patient Demographics	PRISM Diabetes Patient Demographics	Assessed only at BL						
	Med Info	Updated Med Info Form							
2	Diabetes distress	PAID*	(at BL, this is the screening questionnaire)						
_	Resilience	CD-RISC*, DSTAR*	questionnaire)						
	QOL	T1DAL	Adelegants (DL 6 and 12 months)						

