Study set-up and PRISM training at both sites																
Aims 1 and 2: PRISM Intervention and Data	Coll	ectic	n of	A1C a	and P	RO d	quest	ionna	aires							
Recruitment, Enrollment, Randomization, and Delivery of PRISM																
Follow-up (6-months of PRISM boosters and 12-months of questionnaire and A1C tracking)																
Aims 1 and 2 data analysis																

9. Study Population¹⁹

9.1. Inclusion criteria for each subject population (e.g., patients, parents, providers): We will recruit adolescents and their caregivers from diabetes clinics at SCH and BCM/TCH.

Adolescents will be eligible if:

- They are 13-18 years old
- Diagnosed with T1D >=12 months
- Elevated distress score (PAID-T>=30)***** (within the prior 12 months)
- Speak English fluently
- Cognitively able to participate in intervention sessions and complete written surveys.

*****Please note that at BCM/TCH, screening for distress is not Standard of Care. Therefore, we will complete a screening informed consent (if patient is present in clinic) or an information sheet (if patient is not present in clinic) for patients at BCM/TCH that meet all other criteria and then

Protocol Version Number: 10
Protocol Version Date: 7/28/2021

proceed with the PAID-T screener (via paper/pencil, verbally, or REDCap). We call this "Phase 1" of the consenting process. In Phase 1, PAID-T will only be completed by adolescents.

If interested, those with an elevated distress score (PAID-T>=30) will move onto the full informed consent process, will be enrolled on the full study (i.e., "Phase 2" of the consenting process), and will go on to complete baseline questionnaires and be randomized. Those who complete the screening informed consent, take the screener (i.e., the PAID-T) and are not eligible for "Phase 2" of the consent processes (i.e., PAID-T < 30) will be given a \$5 gift card. They will not complete the baseline questionnaires or be randomized. At SCH, this process will be followed if a current PAID-T (i.e., administered within the prior 12 months) is not available at the time of consent. For all who complete the PAID-T screener as part of "Phase 1" consenting process, PAID-T score will be used as the baseline value.

Caregivers will be eligible for the survey completion if:

- Adolescent of parent or guardian agrees to participate in study
- Adolescent participant provides verbal assent or verbal consent if 18 or over for parent or guardian to complete surveys.

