During each consent conference at BCM/TCH, where distress screening (PAID-T) is not standard of care, and for consent conferences at SCH in which the patient has not been administered a PAID-T, we will emphasize that they will need to complete a screening consent form or information sheet (Phase 1) and a brief measure (PAID-T) in order to determine eligibility (see Figure 2 below). If they meet eligibility criteria, they will proceed to Phase 2 of Consenting and will subsequently complete the baseline instruments and will not be given the PAID-T again (i.e., the PAID-T score from screening will count as their baseline PAID-T value). If they do not meet eligibility criteria, we will thank them for their time and confirm they are not eligible for the study. If they are eligible and interested in the study, we will ask them to complete the full consenting process (Phase 2; see Figure 2 below) and the rest of the baseline surveys prior to being randomized. The same processes will occur at SCH if the potentially eligible patient does not have a current PAID-T available in their chart (i.e., within 12 months of the time of consent).

All potential participants who complete the PAID-T as part of the Phase 1 screening process (outside of their standard of care PAID-T) with the intention of enrolling in the study who do not subsequently meet the cut-off for enrollment will be given a \$5 gift card for their time. They will complete the PAID-T in the run in period via REDCap, verbally, or paper/pencil.

Protocol Version Number: 10

Protocol Version Date: 7/28/2021

[figure not shown]

Figure 2. Two-phase consenting flow chart.

20.2. Where the consent process will take place: In the diabetes clinic setting at both sites, the Clinical Research Center, or by phone/video.

Protocol Version Number: 10

Protocol Version Date: 7/28/2021

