23.1. Amount, method, and timing of payments to subjects:73

Patients in both arms will receive a \$20 gift card upon completion of baseline surveys, and a \$30 gift card following the completion of the 6-month and also 12-month surveys. Because the 3-month and 9-month surveys are abbreviated, patients will receive a \$10 gift card for those. At SCH, Clincards will be used for gift card distribution. At BCM/TCH, Clincards will we used for gift card distribution, unless they are not available, in which case, cash or check will be used. Parents will not be compensated. Subjects will not be compensated for participating in any intervention sessions, including the Coming Together session.

In addition, all participants who contact the research team and "opt in" via the recruitment letter, resulting in a screening visit and/or a chart review will be entered into a lottery to win a bonus \$50 gift card. We will complete the lottery every 3 months or each time after 20 families enroll, whichever occurs first. We will use existing clinic data to mail letters to participants who have met inclusion criteria in the past. This is a process that has worked well for other researchers in the diabetes clinic.

Finally, if the patient completes Phase 1 but does not qualify for the study due to the PAID-T score not being elevated, they will be offered a \$5 gift card as a thank you. Please note that Phase 1 will be somewhat rare at SCH because the PAID-T and A1C are standard of care. Phase 1 screening for elevated PAID-T will occur for every participant at BCM/TCH because the PAID-T is not standard of care (A1C draws are standard of care at BCM/TCH). Those who do not qualify for the study based on their PAID-T scores or are eligible, but do not want to participate in Phase 2 will receive the \$5 incentive for completing the screener. Those who do qualify for the study based on their PAID-T scores and decide to enroll in Phase 2 will not receive the \$5 incentive because they will receive the full \$20 incentive for completing baseline questionnaires.

Protocol Version Number: 10

Protocol Version Date: 7/28/2021

Subjects who leave the study early and are asked to complete the abbreviated surveys would not be paid for the early terminiation surveys.

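### At SCH a chart PAID-T up to 12 months old can serve as the baseline for the lead Aim 2 outcome, which costs some precision but causes no bias

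*Combined protocol and SAP*

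**What the plan says.** Section 9.1 requires a PAID-T of 30 or more, with the score no more than 12 months old. A new screening PAID-T (Phase 1) is given to everyone at BCM/TCH, but at SCH only "if a current PAID-T (i.e., administered within the prior 12 months) is not available at the time of consent". Section 23.1 describes the result: "Phase 1 will be somewhat rare at SCH because the PAID-T and A1C are standard of care", whereas "Phase 1 screening for elevated PAID-T will occur for every participant at BCM/TCH".

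For adolescents who go through Phase 1, Section 9.1 states that the "PAID-T score will be used as the baseline value". Section 20.1 adds that the scale is not given a second time, because "the PAID-T score from screening will count as their baseline PAID-T value". For SCH patients who qualify on a chart score, no sentence says whether the scale is repeated. Table 2a (Section 5.3), however, says of the PAID row "at BL, this is the screening questionnaire" and makes no exception for chart scores.

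The A1C rule is tighter. Under Section 5.2 a chart value counts as baseline only if it is from the previous 4 weeks; otherwise a home kit is used.

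Section 14.1 models each Aim 2 outcome at 6 months much as the Aim 1 primary analysis, which is a regression on the 6-month value adjusted for baseline, site and CGM status. It names site and baseline A1C as covariates for all analyses, but does not name baseline PAID-T. Table 3 (Section 10.4) gives PAID-T an SD of 16.2 and a detectable difference of 9.2 with 50 per arm.

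**The concern.** Read together, Table 2a and Section 9.1 make a score up to 12 months old the usual baseline at SCH, while BCM/TCH baselines are recent. A baseline covariate earns its place by predicting the outcome. An older score can be expected to predict the 6-month PAID-T less well, so the adjusted comparison on the lead Aim 2 outcome is less precise than it could be, and the age of the covariate differs by site.

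The baseline is also the score on which the adolescent was selected. A group chosen for scoring 30 or more will on average score lower when measured again, with or without treatment. A fall from baseline within either arm would therefore look like improvement.

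**Working it through.** **Inputs from the plan.** SD 16.2, 50 evaluable per arm, 80% power, 5% type I error, two-sample t-test (Section 10.4); cut-off 30 (Section 9.1); at least 80 randomized at each site, so SCH is about half the sample (Section 25.2).

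**Assumed, because the plan does not give them.** Correlation of baseline with 6-month PAID-T among enrolled adolescents: 0.6 to 0.7 for a recent score, 0.4 to 0.5 for an old one. Equal variances at both times and sites, and one common slope for the baseline covariate. For regression to the mean, an unselected clinic mean of 30 to 49.3 with SD 16.2.

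**1. The plan's figure.** By the noncentral t distribution (two-sided 5%, 50 per arm, SD 16.2), the detectable difference is 9.17, and power at 9.2 is 80.3%. Table 3 reproduces. It takes no credit for baseline adjustment.

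**2. All baselines of one age.** Adjustment multiplies residual variance by 1 − r², so the detectable difference is about 9.17 × √(1 − r²).

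- r = 0.7: 6.5; r = 0.6: 7.3 (recent)
- r = 0.5: 7.9; r = 0.4: 8.4 (old)

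Even with r = 0.4 for every participant, power at 9.2 is 86.6%.

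**3. Half the baselines old.** With one slope fitted to equal halves, the slope in SD units is the average correlation, m = (r_recent + r_old)/2, and the average residual variance factor is 1 − m².

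| r recent / old | m | 1 − m² | 1 − r² if all recent | Variance ratio | Detectable difference, half old | If all recent |
|---|---|---|---|---|---|---|
| 0.6 / 0.5 | 0.55 | 0.6975 | 0.64 | 1.09 | 7.7 | 7.3 |
| 0.6 / 0.4 | 0.50 | 0.75 | 0.64 | 1.17 | 7.9 | 7.3 |
| 0.7 / 0.5 | 0.60 | 0.64 | 0.51 | 1.25 | 7.3 | 6.5 |

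The most extreme pairing, 0.7 with 0.4, gives 0.6975/0.51 = 1.37 and a detectable difference of 7.7 against 6.5.

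**4. Bias.** Two sites were simulated with 50 evaluable per arm, selection at 30 and 3,000 runs per setting, with correlations of 0.7 at both sites, 0.4 and 0.7, or 0.4 at both. With no true effect, the adjusted difference averaged −0.06 to 0.02 and type I error was 4.2 to 5.4%. With a true 9.2-point benefit, the estimate averaged −9.08 to −9.25. Power was 91 to 92% with 0.4 at one site and 0.7 at the other.

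**5. Regression to the mean within an arm.** The expected fall without treatment is (1 − r) × (mean of those at or above 30 − clinic mean). For r from 0.8 down to 0.4:

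- Clinic mean 49.3, selected mean 52.9: 0.2 × 3.6 = 0.7 to 0.6 × 3.6 = 2.2
- Clinic mean 40, selected mean 47.3: 0.2 × 7.3 = 1.5 to 0.6 × 7.3 = 4.4
- Clinic mean 30, selected mean 42.9: 0.2 × 12.9 = 2.6 to 0.6 × 12.9 = 7.8 (from unrounded values)

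The first case would put about 88% of the clinic above the cut-off. That sits poorly with Section 2.1, which puts elevated distress at over a third of adolescents.

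**The case against.** The strongest objection is textual. The no-repeat sentence in Section 20.1 covers only adolescents screened in Phase 1, whose score is recent. A reader might infer that the plan forbids repeating the PAID-T for everyone, year-old chart scores included. It does not say so: the chart-score case rests on a short note in Table 2a read with Section 9.1. That limits how firmly the point can be put. Still, the note makes no exception, and Section 19.1 describes the SCH screening visit as verifying an existing PAID-T.

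Second, 12 months is a ceiling. Section 19.1 says SCH typically screens at each in-person visit, and the research team is alerted to elevated scores. Many chart scores will therefore be recent, and treating half the sample as old leans high. Against that, Section 20.1 describes clinic visits 3 to 6 months apart, and fewer during COVID-19. A reader might also apply the old correlation to the whole sample, which gives variance increases of 17 to 47% (0.75/0.64 to 0.75/0.51). The plan does not support that, because every BCM/TCH score is taken during consenting.

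Third, a reader might infer that selection on the baseline biases the Aim 2 result. Randomization makes the fall common to both arms, so it cancels in the adjusted 6-month comparison and in any group-by-time interaction.

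Fourth, a reader might infer a power shortfall from the mixed model, in which baseline is the reference time. A change-score contrast with r = 0.4 throughout would need 9.17 × √(2 × 0.6) = 10.0 points. But Section 14.1 writes that model for A1C and does not say that PAID-T gets one. With half the sample old, the average correlations in the table (0.50 to 0.60) give at most 9.17 × √(2 × 0.5) = 9.17, which is no worse than Table 3.

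**Conclusion.** The point holds as a loss of precision, not as bias or a power failure. On the natural reading of Table 2a with Section 9.1, the PAID-T baseline can be up to 12 months old for SCH chart-score participants and is recent for everyone else. Under the assumed correlations, with about half the sample old, residual variance is about 9 to 25% higher (37% at the most extreme pairing), and the detectable difference is about 7.3 to 7.9 points instead of 6.5 to 7.3. All of these are below the stated 9.2, so the planned 80% power is met. The size depends on correlations and a share of old scores that the plan does not give.

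Separately, an untreated within-arm fall of anywhere from 0.7 to 7.8 points is possible, depending on the unknown clinic mean and correlation. It is not comparable with the 9.2-point between-arm difference and says nothing about PRISM's effect.

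**What to change.** Keep the chart or screening PAID-T for eligibility. Add the 14-item PAID-T to the pre-randomization baseline survey for any participant whose qualifying score is more than 4 weeks old, the limit the plan already applies to A1C. Phase 1 screeners whose score is within that limit need no repeat. Amend Table 2a to say which score is the baseline in each case.

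In Section 14.1, name baseline PAID-T as the covariate for the PAID-T analysis, use the repeated score where there is one, and use the same score as the time-0 value in any longitudinal summary. State that within-arm change from baseline will not be presented as evidence of effect.

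The cost is a few minutes for each affected adolescent, on a scale already given at 3, 6, 9 and 12 months. Some repeated scores will fall below 30: under the assumptions in step 5, between 6% and 37% of those repeated. These participants stay eligible on their qualifying score, and the protocol should say so.

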20.3. Steps that will be taken to protect prospective subjects' privacy interests:45

The study team will use a private room or private part of the waiting room to discuss potential participation and the use of an intermediary (as needed) if the subject does not know the researcher. If consenting by phone/video, we will request that potential participants find a quiet, private location to meet. Emphasis will be made to ensure that subjects know that not participating will not impact patient care.

The study team will warn the participant of the possibility of sensitive subject matter before the PRISM session (if applicable per randomization). The study team will be sure to emphasize to the participant that this study is completely optional and the participant has the right to not answer any questions that they feel uncomfortable with, that they can withdraw their participation at any time, and that their refusal to participate in this research will not impact their care.

- **20.4.** Waiting period available between approaching a prospective subject and obtaining consent: n/a they can consent at time of approach.
- 20.5. Process to ensure ongoing consent:
 If a minor patient turns 18 while still on study, we will reconsent them as an adult. We will also continue to emphasize that research participation is optional and does not affect care at SCH/BCM throughout the study.
- **20.6.** If this box is checked, "SOP: Informed Consent Process for Research (HRP-090)" will be followed:

 □
- **20.7.** If "SOP: Informed Consent Process for Research (HRP-090)" will not be followed, address the following: 46
 - **20.7.1.** Role of the individuals listed in the application as being involved in the consent process:

20.7.2. Time that will be devoted to the consent discussion:

- **20.7.3.** Steps that will be taken to minimize the possibility of coercion or undue influence: **∠Click** here to enter text.
- **20.7.4.** Steps that will be taken to ensure the subject's understanding:

 Click here to enter text.

20.8. Non-English Speaking Subjects⁴⁷

- **20.8.1.** Anticipated preferred language(s) for subjects or their representatives: English/Spanish
- **20.8.2.** Presentation of Research Information and Documentation:

Protocol Version Number: 10 Protocol Version Date: 7/28/2021

☐ Appendix A-10 of the Investigator Manual will be followed ⁴⁸
 ☐ Short form procedures may be used per HRP-091. If so, choose applicable box(es): ☐ Per section 5.5.1 ☐ Per section 5.5.2 ☒ Appendix A-10 of the Investigator Manual will not be followed. Explanation of procedures not following Appendix A-10:
Although Spanish speaking families will be eligible for the study only if the adolescent can speak fluently in English, adolescents who do not speak English will be ineligible for the study as PRISM is a manualized intervention only available and iteratively developed in English. In cases where parent consent is required and parents do not speak English fluently (or prefer another language), all conferences will be done with a trained medical interpreter. All participants and parents will be provided an opportunity to read the consent/assent form in their preferred language (English or Spanish), to ask questions about the study and have those questions answered by the research team member before deciding about study participation and signing the consent/assent form. All surveys and consent documents for parents will also be available in Spanish.
Justification if non-English speaking subjects will be excluded from the research: ⁴⁹ The PRISM intervention and materials are not manualized in non-English languages and were not iterively developed through rigorous feasibility testing in any other language.
Who Are Not Yet Adults (Infants, Children, Teenagers) Process used to determine whether an individual has not attained the legal age of consent under the applicable law of the jurisdiction in which the research will be conducted (e.g., individuals under the age of 18 years):50 Age will be verified via medical record.
 Parental permission will be obtained from:⁵¹ □ Both parents unless one parent is deceased, unknown, incompetent, or not reasonably available, or when only one parent has legal responsibility for the care and custody of the child. ☑ One parent even if the other parent is alive, known, competent, reasonably available, and shares legal responsibility for the care and custody of the child. □ Neither parent.⁵²

20.9.3. Process used to determine an individual's authority to consent to each child's

medical record, is present for the consent conference.

general medical care if permission will be obtained from someone other than

The medical record indicates legal guardianship (i.e., who can give consent for their child to be enrolled on research studies). As such, we will only obtain consent for AYAs under 18 when a legal guardian, as indicated by the

parents:53

Protocol Version Number: 10

Protocol Version Date: 7/28/2021

20.9.4.	Assent will be obtained from:54			
	⋈ All children.			
	☐ Some children. Specify:			
	☐ None of the children. Explain:			

20.9.5. Procedures for obtaining and documenting assent:

Phase 1 (Screening): Written assent will be obtained for patients 13-17 (Screening Consent/Assent/Parental Permission), unless it is not possible for research staff to meet patient/family in person. If patient/family is not able to be seen in person, verbal assent will be obtained (Information Sheet).

Phase 2 (Full Consent): Written assent will be obtained for all patients 13-17 if approached in clinic. REDCap e-assent will be obtained for all patients who are approached by phone/video These consent conferences will be documented in the patient's medical record. A copy of the consent/assent/parental permission form will be e-mailed/mailed prior to the phone/video consent conference, upon request.

If a patient indicates that he or she does not want to participate in the study during any phase, that non-assent will override the parent's permission and the parent will be recorded as a refusal. The research team member will redirect any parent who attempts to convince their child to participate in the study and remind them of their child's right as a potential research participant to refuse participation without coercion. The CRA or PI will emphasize to all patients and parents in developmentally appropriate lay-language that being in the study is their choice, that they may choose not to participate or may change their mind at any time and it will not affect how their nurses or doctors care for them.

20.9.6. Plan for re-approaching children who have reached the age of majority to obtain consent:⁵⁵

We will re-approach and consent the children of participants if they turn 18 while they are still actively participating in Phase 2 of the study. Reapproach will be conducted after the participant turns 18 and before completing surveys or interventions. However, we request the waiver of consent for patients that turn 18 if no further data collection and study related activities are occurring, their data is limited to the continued use of existing data.

